### 3.8 Risk-to-benefit rationale

Based on a review of the Use, Design, and Process FMEAs, the potential benefits of use of the WaveCrest LAA Occlusion System outweigh the risks. Percutaneous LAA occlusion may offer an alternative to physicians who are caring for subjects with AF who are at high risk for both bleeding and stroke.

## 4. PURPOSE

### 4.1 Name and Intended Use

The Coherex WaveCrest Left Atrial Appendage Occlusion System is a percutaneous transcatheter device intended to be used for closure of the left atrial appendage (LAA).

#### 4.1.1 Indications for Use

The Coherex WaveCrest Left Atrial Appendage Occlusion System is indicated in subjects who have all of the following:

	Title: The WAVECREST 2 Trial  Clinical Investigational Plan	Doc. #: CHX_IP014	Rev: H
---	--	-----------------------------	------------------

- Non-valvular paroxysmal, persistent, or permanent atrial fibrillation
- LAA anatomy amenable to treatment by percutaneous techniques
- Risk factors for potential thrombus formation in the LAA

## 4.2 Scope of Trial

The WAVECREST 2 trial is a prospective, multicenter, randomized, active controlled, clinical trial to evaluate the safety and effectiveness of the Coherex WaveCrest Left Atrial Appendage (LAA) Occlusion System for the reduction in rate of ischemic stroke or systemic embolism in subjects with non-valvular atrial fibrillation who are at increased risk for stroke and have an appropriate rationale to seek a non-pharmacologic alternative to chronic oral anticoagulation.

Subjects will be randomized in a 1:1 ratio to the Treatment Arm (Coherex WaveCrest LAA occlusion system) or the Control Arm (Boston Scientific’s Watchman LAA occlusion system). Randomization will be stratified by site and CHA2DS2-VASc score ≤ 4 vs. > 4. The trial is designed to demonstrate that safety and effectiveness of the WaveCrest device are non-inferior to the Watchman device. The subject, the implanting Investigator and catheterization laboratory staff will have knowledge of the assigned treatment. Trial personnel and the board-certified study Neurologist who will perform follow-up assessments for ascertainment of the primary effectiveness endpoint will be blinded to the randomization assignment and implanted device to the extent possible.

An independent Clinical Events Committee (CEC) will be blinded to the treatment assignment and will adjudicate protocol-defined events, including primary and secondary endpoints, death (cardiovascular vs. non-cardiovascular), and bleeding category. An independent Data Monitoring Committee (DMC) will monitor the safety of trial subjects and will review data at interim analyses. The DMC may provide recommendations for early regulatory filing of trial results upon review of interim analyses. An independent Echocardiography Core Laboratory (ECL) will review transesophageal echocardiograms (TEE) to assess LAA closure and device thrombus and will review post-stroke TEEs to ascertain the mechanism of stroke. Transthoracic echocardiograms (TTE) will be assessed by the core lab to assess for post-implant pericardial effusion.

### 4.2.1 Trial Size

Up to 1,550 subjects will be randomized and up to 500 subjects may be treated as roll-ins (total enrollment up to 2,050) at up to 100 investigational sites in North America, Europe, Australia and Asia. Up to 50% of subjects may be randomized outside the United States. Each investigational site may not randomize more than 15% of the total randomized subjects. Auxiliary sites (i.e., additional physical locations that are part of a clinical site) may be used to help in recruitment and follow-up activities but will not be utilized for protocol-specific assessments (e.g., subject consent, TEE, QVSFS, QoL, Neurological assessment, etc.), which will be performed only by sites that have been properly trained and have obtained the required IRB/EC approvals to conduct study-specific activities.

	Title: The WAVECREST 2 Trial  Clinical Investigational Plan	Doc. #: CHX_IP014	Rev: H
---	--	-----------------------------	------------------

#### 4.2.2 Duration

Enrollment is expected to last between 2 and 3 years, and the maximum follow-up duration is 5 years, for a total possible trial duration of approximately 8 years.

### 4.3 Endpoints

#### 4.3.1 Primary Endpoint

This trial is designed to evaluate the safety and effectiveness of the Coherex WaveCrest LAA occlusion device to the Boston Scientific Watchman LAA occlusion device by demonstrating that the device is non-inferior to the Watchman Device with respect to the primary safety and effectiveness endpoints. If non-inferiority is demonstrated, superiority will be evaluated.

- The primary effectiveness endpoint is the composite rate of ischemic stroke or systemic embolism at 24 months.
- The primary safety endpoint is the composite rate of all cause death; procedure- or device-related complications requiring percutaneous or surgical intervention, including embolization of a LAA closure device, drainage of pericardial effusion, or repair of cardiac or vascular structures through 45 days post-procedure; or major bleeding.

#### 4.3.2 Secondary Effectiveness Endpoints

- Rate of LAA closure, defined as a gap of  $\leq 5$ mm as assessed by TEE, at 45 days
- Incidence of ischemic stroke or systemic embolism with the WaveCrest device in comparison to the CHADS2 and CHA2DS2-VASc imputed risk of ischemic stroke or systemic embolism in the absence of anticoagulant therapy. No claims will be made on this endpoint.

### 4.4 Inclusion and Exclusion Criteria

#### 4.4.1 Inclusion Criteria

Subjects must meet ALL of the following inclusion criteria to be considered eligible for the clinical trial.

1. Documented evidence of paroxysmal, persistent, or permanent non-valvular atrial fibrillation
2. At least 18 years of age
3. Calculated CHADS2 score  $\geq 2$  or CHA2DS2-VASc score  $\geq 3$  (See **Appendix II** for calculation of CHADS2 and CHA2DS2-VASc scores)
4. Indication for warfarin therapy with an appropriate rationale to seek a non-pharmacologic alternative to chronic oral anticoagulation
5. Willing and able to comply with post-implant anticoagulation and antiplatelet regimen
6. Willing to participate in the required follow-up visits and tests
7. Subject has been informed of the nature of the trial, agrees to its provisions and has provided written informed consent as approved by the IRB/EC at the site

	Title: The WAVECREST 2 Trial  Clinical Investigational Plan	Doc. #: CHX_IP014	Rev: H
---	--	-----------------------------	------------------

#### 4.4.2 Exclusion Criteria

If ANY of the following clinical exclusion criteria is met, the subject must be excluded from the clinical trial.

1. Atrial fibrillation (AF) due to a reversible cause (e.g. thyrotoxicosis or postoperative)
2. Known contraindication and/or allergy to warfarin, nickel, aspirin, intravenous contrast or P2Y12 inhibitors (clopidogrel, ticagrelor, and prasugrel), which cannot be adequately pre-medicated or desensitized
3. Conditions other than AF requiring long-term anticoagulation therapy
4. Contraindications for percutaneous catheterization procedures
5. Prior surgical LAA occlusion/exclusion or implanted with LAA occlusion device, or any prior attempt of such procedures
6. Prior percutaneous or surgical closure of a patent foramen ovale or atrial septal defect
7. Inability or unwillingness to take oral anticoagulation for 45 days post-procedure
8. New York Heart Association (NYHA) Class IV heart failure
9. Prior cardiac transplant, history of mitral valve replacement or transcatheter mitral valve intervention, or any mechanical valve implant
10. History of symptomatic carotid, intervertebral, or intracranial artery occlusion or stenosis without revascularization with the exception of known occlusion without symptoms > 6 months
11. mRS score  $\geq 4$
12. Chronic resting heart rate  $\geq 110$  bpm
13. Congenital or other clinically significant cardiac anomalies requiring cardiac surgery or interventional repair
14. Stroke or transient ischemic attack (confirmed by Neurologist) within 60 days prior to enrollment
15. Myocardial infarction within 60 days prior to enrollment
16. Sepsis or any active infection requiring oral antibiotic therapy within 14 days or intravenous antibiotic therapy within 30 days prior to enrollment
17. Surgical or interventional cardiovascular and non-cardiovascular procedure including cardioversion within 30 days prior to enrollment or AF ablation within 60 days prior to enrollment or any planned general surgery or interventional procedure within 90 days after enrollment or any planned cardiac surgery.
18. On renal replacement therapy, serum creatinine > 3.0 mg/dl (265  $\mu$ mol/L) or calculated creatinine clearance < 25 ml/minute
19. Thrombocytopenia (<60,000 platelets/mm^3), leucopenia (white blood cell count < 3,000 cells/mm^3), or anemia (hemoglobin concentration < 10 grams/deciliter)
20. Any medical disorder or psychiatric illness that would interfere with successful completion of the trial
21. Currently participating in an investigational drug trial or another device trial that has not completed the primary endpoint (trials requiring extended follow-up for products that are commercially available are not considered investigational trials). Concurrent enrollment in the ACC LAAO Registry is permitted.

	Title: The WAVECREST 2 Trial  Clinical Investigational Plan	Doc. #: CHX_IP014	Rev: H
---	--	-----------------------------	------------------

22. Subject belongs to a vulnerable population (see definition in **Appendix I: Acronyms and Definitions**)
23. Any condition that would reduce life expectancy to less than 2 years
24. Women of childbearing potential who are, or plan to become pregnant during the time of the trial (method of assessment per physician discretion)

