	
 
10. History of symptomatic carotid, intervertebral, or intracranial artery occlusion or stenosis without revascularization with the exception of known occlusion without symptoms > 6 months
 
11. Modified Rankin Scale Score <math>\geq</math> 4
 
12. Chronic resting heart rate > 110 bpm
 
13. Congenital or other clinically significant cardiac anomalies requiring cardiac surgery or interventional repair
 
14. Stroke or transient ischemic attack (confirmed by Neurologist) within 60 days prior to enrollment
 
15. Myocardial infarction within 60 days prior to enrollment
 
16. Sepsis or any active infection requiring oral antibiotic therapy within 14 days or intravenous antibiotic therapy within 30 days prior to enrollment
 
17. Surgical or interventional cardiovascular and non-cardiovascular procedure including cardioversion within 30 days prior to enrollment or AF ablation within 60 days prior to enrollment or any planned general surgery or planned interventional procedure within 90 days after enrollment or any planned cardiac surgery
 
18. On renal replacement therapy, serum creatinine > 3.0 mg/dl (265 <math>\mu</math>mol/L) or calculated creatinine clearance < 25 ml/minute
 
19. Thrombocytopenia (<60,000 platelets/mm^3), leucopenia (white blood cell count < 3,000 cells/mm^3), or anemia (hemoglobin concentration < 10 gram/deciliter)
 
20. Any medical disorder or psychiatric illness that would interfere with successful completion of the trial
 
21. Currently participating in an investigational drug trial or another device trial that has not completed the primary endpoint (trials requiring extended follow-up for products that are commercially available are not considered investigational trials). Concurrent enrollment in the ACC LAAO Registry is permitted.
 
22. Subject belongs to a vulnerable population (see definition in Appendix I: Acronyms and Definitions)
 
23. Any condition that would reduce life expectancy to less than 2 years
 
24. Women of childbearing potential who are, or plan to become pregnant during the time of the trial (method of assessment per physician discretion)
 

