### 4.5.2 Point of Enrollment

Subjects will be considered enrolled and followed from the time an informed consent form is signed. Subjects will be documented as a roll-in subject, a randomized subject, or a screen failure. Enrolled screen failures will be excluded from the randomized cohort. Any adverse events in these subjects will be documented in eCRFs. Intent-to-treat will be established when they have completed screening, met all inclusion criteria, none of the exclusion criteria, and are randomized.

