### 6.1 Baseline Evaluation and Randomization/Roll-in

The Baseline time period begins with subject enrollment (informed consent) and ends with either vascular access in the interventional procedure (roll-in subjects) or randomization (randomized subjects).

Sites must receive approval from Sponsor to begin implantation procedures. This approval should be retained in the site regulatory binder. Sponsor personnel must be present for all roll-in procedures. Once a site begins randomizing subjects in the trial (“randomization phase”), no roll-in subjects will be permitted for that site.

All subjects are considered enrolled when the Informed Consent is signed. Standard of care tests or assessments may be used to evaluate Inclusion and Exclusion Criteria if the test or assessment meets the requirements of this CIP.

The following Baseline steps are recommended to be performed within 30 days **prior to** randomization but must be completed within 90 days **prior to** randomization (or within 90 days prior to treatment of roll-in subject):

- Document medical history (if not previously documented).
- Document appropriate rationale to seek a non-pharmacologic alternative therapy
- Perform physical exam
- Administer Quality of Life (QoL) questionnaire (see **Quality of Life Questionnaire - SF-36**).
- Blood work to document CBC (HGB, WBC, platelets), serum creatinine with INR and pregnancy (as necessary)
- CHADS2 and CHA2DS2-VASc score (see **Appendix II** for calculation of CHADS2 and CHA2DS2-VASc scores).
- Calculate HAS-BLED score (see **Appendix II** for calculation of HAS-BLED score)
- A trial staff member must administer the QVSFS to the subject (see **Appendix III: Questionnaire for Verifying Stroke-Free Status**).
- All subjects must undergo a NIHSS and a mRS. Both must be administered by board-certified study Neurologist or trained and certified trial personnel (Appendix IV: Neurologic Assessments)
- If the subject has a history of stroke or TIA or if the baseline QVSFS score is > 0 the subject must be seen by a board-certified study Neurologist, including review of the following:
  - Brain imaging (MRI unless contraindicated, then CT)
    - NOTE: If an imaging study is available following the prior stroke or TIA, a new study is not required per study Neurologist’s discretion
  - Completed NIHSS and mRS.

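### The recent-event exclusions count back from consent, so a stroke, MI, treated infection or unplanned procedure between consent and randomization does not trigger its own criterion

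*Protocol*

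**What the plan says.** Protocol 4.4.2 lists four dated recent-event exclusions, and the Synopsis repeats them:

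- Exclusion 14: "Stroke or transient ischemic attack (confirmed by Neurologist) within 60 days prior to enrollment".
- Exclusion 15: "Myocardial infarction within 60 days prior to enrollment".
- Exclusion 16: "Sepsis or any active infection requiring oral antibiotic therapy within 14 days or intravenous antibiotic therapy within 30 days prior to enrollment".
- Exclusion 17, look-back part: "Surgical or interventional cardiovascular and non-cardiovascular procedure including cardioversion within 30 days prior to enrollment or AF ablation within 60 days prior to enrollment". Its forward part covers "any planned general surgery or interventional procedure within 90 days after enrollment" and any planned cardiac surgery.

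The reference date is defined twice. Section 4.5.2: "Subjects will be considered enrolled and followed from the time an informed consent form is signed". Section 6.1: "All subjects are considered enrolled when the Informed Consent is signed".

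Section 6.1 then describes a period that starts at that date: "The Baseline time period begins with subject enrollment (informed consent) and ends with either vascular access" for roll-ins, or with randomization for randomized subjects. Baseline steps are recommended within 30 days before randomization and must fall within 90. Under Section 6.2, treatment of randomized subjects is recommended within 7 days of randomization and required within 14. For roll-ins, treatment within 90 days of enrollment is only recommended.

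Section 4.4.3 dates the echocardiographic exclusions differently. They are assessed before randomization, or before the procedure for roll-ins.

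**The concern.** The clinical look-backs and the echocardiographic exclusions run on different clocks, and no reason is given. The clinical clock stops at consent, which can be weeks before the subject is randomized and implanted. An event inside that interval is later than enrollment, so it cannot be prior to enrollment.

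Two things are at stake. The first is subject protection. Section 7.2 says the eligibility criteria exist to keep out subjects for whom use of the device carries unreasonable risk, yet a site could follow the text exactly and implant a subject whose stroke or MI was more recent than the stated window. The second is the cleanness of the endpoints. Early recurrent strokes or deaths that stem from a fresh pre-implant event would count in the effectiveness and safety composites without saying anything about either device.

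**Working it through.** The plan gives no figure on this point, so the check is a reading of dates followed by interval arithmetic.

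**Dates.** Two subjects both consent on day 0 and are randomized on day 35.

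- Subject A has a non-disabling stroke on day −25. It is within 60 days before consent, so exclusion 14 applies. At randomization the stroke is 25 + 35 = 60 days old.
- Subject B has the same stroke on day +25. It is not before consent, so exclusion 14 does not apply. At randomization the stroke is 35 − 25 = 10 days old.

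The criterion stops the older event and lets the newer one through.

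**Share of the look-back left uncovered.** Let G be the days from consent to randomization, T the days from randomization to implant, and W the look-back length (60, 30 or 14 days). Measured back from implant, the part of W that falls after consent is min(G + T, W) / W. Setting T = 0 gives the share at randomization.

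| G | T | G + T | W = 60 | W = 30 | W = 14 |
|---|---|---|---|---|---|
| 7 | 0 | 7 | 12% | 23% | 50% |
| 7 | 14 | 21 | 35% | 70% | 100% |
| 30 | 0 | 30 | 50% | 100% | 100% |
| 30 | 14 | 44 | 73% | 100% | 100% |
| 60 | 0 | 60 | 100% | 100% | 100% |
| 90 | 14 | 104 | 100% | 100% | 100% |

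T = 14 is the stated maximum. G is not stated anywhere. The values 7 to 90 are assumptions, with 30 and 90 matching the recommended and maximum age of baseline steps. G = 90 corresponds to consent on the date of the oldest permitted step. A subject treated for baseline thrombus after consent has G of at least 6 weeks (42 days), which alone takes 42/60 = 70% of the 60-day window.

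**Forward window.** The cover left at implant is 90 − (G + T) days. For G = 30 and T = 14 it is 90 − 44 = 46 days. For G = 60 and T = 14 it is 90 − 74 = 16 days. For G = 90 and T = 14 it is 90 − 104 = −14, so the window has closed two weeks before implant.

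**Clauses that might close the gap.** Section 4.5.2 requires that randomized subjects meet none of the exclusions. Section 6.1 allows treatment only while eligibility still holds, in a paragraph about echocardiographic screening of roll-ins. Both refer back to criteria whose reference date is consent, so re-applying them later gives the same answer.

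**After re-dating to randomization.** The uncovered share at randomization is 0 for any G. At implant up to 14 days remain: 14/60 = 23%, 14/30 = 47% and 14/14 = 100%.

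**The case against.** The best defense is that other text catches many of these subjects. Several exclusions carry no date: contraindication to catheterization (4), symptomatic carotid or intracranial disease (10), mRS of 4 or more (11), laboratory limits (18, 19), an interfering medical disorder (20), limited life expectancy (23) and intracardiac thrombus on TEE, which Section 6.2 checks again before implant. Inclusion 5 and exclusion 7 could apply where planned surgery would interrupt the post-implant regimen. Adverse events are recorded from consent, serious ones reach the sponsor within 72 hours, and Section 6.12 provides a route to repeat NIHSS and mRS. The Section 6.1 clause shows an intent that eligibility persist to treatment.

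Much of this stands and limits the point. It does not remove it. A non-disabling stroke, a TIA, an uncomplicated MI or a treated infection need not meet any undated criterion, some of those criteria rest on investigator judgement, and no rule ties a recorded post-consent event to eligibility.

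Three stronger readings are tempting, and the documents do not support them.

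- A reader might infer that every procedure after consent escapes. Exclusion 17 already covers procedures planned within 90 days after enrollment and any planned cardiac surgery. Only unplanned procedures, or ones planned after consent, fall through the look-back.
- A reader might apply the Table 1 stroke rates to an assumed gap: 1,550 × 0.032 × 30/365 = 4.1 up to 1,550 × 0.067 × 90/365 = 25.6. That counts all strokes in the gap, not subjects then randomized soon after one. It also ignores anticoagulation before implant, and its lower end is not a floor (a 7-day gap at 3.2% gives about 1).
- A reader might conclude that the non-inferiority ratios are materially pulled toward 1. The direction is plausible if such events occur equally in both arms, but the number of such events is unknown.

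**Conclusion.** The point holds in a limited form. The look-backs in exclusions 14 to 17 end at consent, and an event of the named kind between consent and randomization does not meet its own criterion. This follows from the protocol's definitions and needs no outside figure. The uncovered share depends on a gap that the plan does not cap as such: the 90-day limits apply to baseline steps and to thrombus treatment. Where consent and randomization are close together, the exposure is small. Section 6.1 also lets standard-of-care tests serve as baseline, so consent may come later than the oldest step.

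The forward window has the same reference date and can close before, or soon after, a late implant. That needs a gap near the upper end of the range.

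Neither the number of subjects affected nor any effect on the 1.75 ratio tests can be estimated from the documents. The case for acting rests on a stated rule that gives the wrong result, and on a cheap remedy.

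**What to change.** In Protocol 4.4.2 and the Synopsis, leave the window lengths as they are and count the look-backs in exclusions 14 to 17 to randomization, or to the procedure for roll-ins. Section 4.4.3 already uses that reference point, and it fits the timing in Sections 6.1 and 6.2. Have sites re-confirm these items in the EDC at randomization. Because up to 14 days remain before implant, state whether status is also re-confirmed at the Treatment Visit. The sponsor should reconcile the forward part of exclusion 17 with the implant timing; how that clinical window should run is for the sponsor to decide.

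The cost is a wording change in two lists and one EDC check. A few subjects will be delayed or become screen failures.

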#### 4.4.3 Echocardiographic Exclusion Criteria

The following echocardiographic exclusion criteria must be assessed prior to randomization (or prior to the procedure for roll-in cases). The transesophageal echocardiogram (TEE) must be performed up to 90 days before, including just prior to, randomization (or the procedure for roll-in cases). If ANY of the following echocardiographic exclusion criteria is met, the subject must be excluded from the clinical trial.

1. Estimated left ventricular ejection fraction < 30%
2. Mitral valve stenosis defined as valve area < 1.5cm^2, mean gradient > 6mmHg, or any mitral valve deformity consistent with rheumatic valvular disease
3. Aortic valve stenosis defined as valve area ≤1.0cm^2 or mean gradient >30mmHg
4. Circumferential pericardial effusion > 10mm, loculated pericardial effusion with largest dimension > 10mm, or symptomatic pericardial effusion of any size
5. Evidence of intracardiac thrombus
6. Cardiac tumor or myxoma
7. Atrial septal defect that warrants closure
8. Complex atheroma in the ascending aorta or aortic arch as evidenced by mobile plaque
9. Left Atrial Appendage size and shape are unsuitable for closure with a WaveCrest or Watchman device

